## VI. Study Procedures/Study Design

**Group 1: Usual care.** Participants in this group will receive standard hospice care and bereavement support according to the policy of each hospice agency. We considered using an attention match control but chose “usual care” instead, as prior research demonstrated that using attention match control in a behavioral randomized trial is problematic, especially for outcomes such as depression (our primary outcome of interest) and anxiety. This literature advocates that controlling for attention is not necessary and counterproductive in some behavioral intervention trials. Once assigned to an arm, the participant remains in that arm for the entire study, from active caregiving through bereavement. We will not randomize a second time at bereavement. Control group participants will complete study measures electronically through the REDCap system at the same intervals as the intervention group.

**Group 2: Caregiver Speaks intervention group.** Participants in this group will receive usual care plus the Caregiver Speaks intervention. They will participate in a Facebook group to share their photos and personal stories. During the initial zoom meeting, a research staff person will 1) train caregivers how to set-up and use Facebook, if needed, 2) discuss elements of their story and identify artifacts they may wish to feature in their photo-elicitation process, and 3) enroll them in the pre-bereavement caregiver private Facebook group. Caregivers will participate in this group until the PLWD dies, at which time they will transition (one month) into a bereavement focused group. The bereavement group will include the same components, but the focus of the photos and conversation will be on bereavement. Table 1 provides a summary of the study and intervention participation, as well as the data collection schedule. We will provide caregivers a printed reference guide for using Facebook, including group rules and common Facebook terms, based on materials we have used extensively in our preliminary work.

In an effort to increase retention of participants, the interventionist will now add a follow-up/technical assistance phone call with each NEW intervention participant after they have completed one full week of the intervention to assess the following:

- a. whether or not there are barriers to accessing/using Facebook.
- b. whether or not caregivers are able to share photos.

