**Table 2: Aims, Hypotheses, and Associated Measures**

*Pre-bereavement measures collected at baseline, 14, 30, 90, and 150 days (follow-up data collection post 150 days will occur every 6 weeks until participant transitions to bereavement). Post-death measures collected at transition, 14, 30, 90, 150 and 180 days. During study wind down, participants will complete their final data collection measure based on where they are at in the intervention (e.g., if a participant is on day 90 of 150, they will complete day 90 survey as their final measure).*

Specific Aim	Hypotheses (H) and Research Questions (RQ)	Instruments and Variables	Description
Aim 1: Determine the efficacy of the Caregiver Speaks intervention in reducing depression and anxiety among hospice family caregivers of PLWD.	RQ1: What is the effect of the Caregiver Speaks intervention on caregivers' depression, anxiety (outcomes of interest)? H1a: Family caregivers receiving the intervention will	Primary Outcome: Depression Patient Health Questionnaire (PHQ-9) Secondary Outcome: Anxiety Generalized	PHQ-9: a 9-item screening tool and severity measure for depressive mood.  Internal Consistency: .87 

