### **Data Analysis Plan:**

**Statistical Assumptions.** We will examine linearity and homoskedasticity by calculating and plotting residuals and Cook's distance for all models. Where data are missing, we will use the Last Observation Carried Forward (LOCF) missing data imputation technique, given that < 30% of data were missing for any particular subject in our prior work. If the proportion of missing data is higher, we will use regression based multiple imputation. Little's MCAR test (missing completely at random) will be used to test that missingness is in no way related to the intervention. Because the sample size is relatively large, we expect that known and unknown confounders will be distributed evenly among the two randomized groups. Additional confounders will only be introduced as covariates if we find evidence of imbalance between groups at baseline. We acknowledge that this study is not powered to detect small interaction effects.

We will test whether randomization created balanced groups by comparing baseline measures and demographic characteristics, using chi-square or t-test analysis for categorical or continuous variables, respectively. Variables that differ significantly between groups will be included in regression models as potential confounders. We will include time from study enrollment to the last observation as a covariate, as well as hospice agency. We will report estimates with 95% confidence intervals. To draw inferences from our study for the likely benefit to an equivalent population, where the intervention under trial is a model of service delivery, all analyses of outcomes will be by intention-to-treat. The intention-to-treat analysis, consistent with the objectives of a pragmatic trial, will minimize the influence of "informative missingness" of the data and preserve groups' comparability.

**Statistical Analysis.** H1a: Family caregivers receiving the intervention will report lower levels of depression and anxiety (outcomes of interest), which is facilitated by higher social support (mediating variable) than those in the control group during active caregiving.

H1b: Family caregivers receiving the intervention will report lower levels of depression and anxiety (outcomes of interest), which is facilitated by higher social support (mediating variable) than those in the control group during bereavement.

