We will examine differences between longitudinal profiles of the two study groups for each of the outcomes (PHQ-9, GAD-7, and grief intensity). We will use linear mixed effect repeated measurement (MMRM) (see model below). This will allow us to draw inferences about how our outcome measures (PHQ-9, GAD-7 and grief intensity) change over time ( $\text{slope} = \beta_{(1,T)}$  and  $\beta_{(1,C)}$ ) between the two study groups. Mixed models are able to accommodate differing numbers of measurements at varying time intervals for participants. Additionally, we will examine how social support mediates our outcomes of interest (depression, anxiety, and grief intensity). As described above, we will also include covariates where indicated.

$$\begin{aligned}
 Y_{ij} &= \beta_{-}(0,T) + \beta_{-}(1,T) t_{ij} + b_{-}oi + e_{-}ij && \text{for Treatment group} \\
 &= \beta_{-}(0,C) + \beta_{-}(1,C) t_{ij} + b_{-}oi + e_{-}ij && \text{for Control group}
 \end{aligned}$$

Where  $Y_{ij}$  represent the depression/anxiety score of the  $i^{th}$  subject at the  $j^{th}$  time,  $\beta_{-}(1,T)$  and  $\beta_{-}(1,C)$  represent the slopes for the treatment and control group respectively with intercepts that vary about the respective mean intercepts  $\beta_{-}(0,T)$  and  $\beta_{-}(0,C)$ .

H1c: Among the intervention group, family caregivers with higher baseline depression scores will experience a larger reduction in depression compared to those with less depression at baseline.

A multiple linear regression model will be used as for H1a above to examine the modifying effect of baseline PWBS score. If the  $\beta_2$  coefficient is negative and statistically significant, we will conclude that the effects of the Caregiver Speaks intervention are conditional on baseline perceptions after adjusting for duration of caregiving (time).

$$\text{Last post-baseline Anxiety/depression} = \beta_0 + \beta_2 * [\text{baseline anxiety/depression}] + \beta_3 * [\text{time}]$$

H2: Bereaved family caregivers receiving the intervention will report lower grief intensity (outcome of interest) than those in the control group.

A linear mixed effect model similar to those used for H1a and H1b will be used to examine H2, where the  $Y_{ij}$  will represent the grief intensity score for a subject of the  $i^{th}$  subject at the  $j^{th}$  time.

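### H1b and H2 predict lower levels in bereavement, but the protocol names only a slope comparison, and the SAP's last-measure level contrast conflicts with it

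*Protocol*

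**What the plan says.** **Hypotheses.** In the protocol's Data Analysis Plan, H1a (active caregiving) and H1b (bereavement) each state that intervention caregivers "will report lower levels of depression and anxiety (outcomes of interest") than controls. H2 makes the same kind of claim for grief intensity. All three concern levels.

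**Protocol analysis.** The stated aim is broad: "We will examine differences between longitudinal profiles of the two study groups for each of the outcomes". The method follows: "We will use linear mixed effect repeated measurement (MMRM) (see model below"). The printed model is linear in time, with a separate mean intercept and slope for each arm and a random intercept per caregiver. The inference attached to it is: "This will allow us to draw inferences about how our outcome measures (PHQ-9, GAD-7 and grief intensity) change over time", with the two slope coefficients given in brackets. For grief: "A linear mixed effect model similar to those used for H1a and H1b will be used to examine H2".

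**Timing.** Assignment is made before the death and carries through: "We will not randomize a second time at bereavement" (Group 1: Usual care). Table 2 gives the collection schedule: "Post-death measures collected at transition, 14, 30, 90, 150 and 180 days". The Data Safety Monitoring Plan gives a different one, every 30 days. Neither says which visits enter which model, or whether time runs from enrolment or from the death.

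**SAP.** Statistical Assumptions takes the final bereavement measure for H1b and describes the approach as a last-observation analysis. Statistical Analysis, covering H1a, H1b and H2, then announces repeated-measures mixed models with inference on slopes. The equation it prints is a one-record regression of the last measure on study group, baseline measure and time since enrolment. The SAP is dated January 2019. The protocol carries changes dated 2021 and 2022.

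**The concern.** A difference in slopes is not a difference in levels. At enrolment the distinction matters less, because that visit precedes any effect: if it is in the model, a later level difference has to show partly as a slope. In bereavement that protection can be lost. Intervention caregivers have been exposed since before the death, so the arms may already differ at the transition visit. With a free intercept per arm, a difference present at the first modelled visit goes into the intercepts.

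PHQ-9 is the primary outcome, and H1b is one of its two between-arm hypotheses. Following the named inference on bereavement visits alone could report no effect when depression is lower throughout. It could also report a result favouring control when a real benefit shrinks but persists. With a slope analysis in one document and a last-measure analysis in the other, the trial has two competing tests of the same hypotheses and no rule for choosing between them.

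**Working it through.** The plan gives no power figure for a slope or a level contrast in bereavement, so there is none to reproduce.

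**Inputs from the protocol.** 468 caregivers and 30% attrition (V. Number of Subjects): 468 x 0.7 / 2 = 163.8, taken as 164 per arm. Two-sided 5%. Bereavement visits at days 0 (transition), 14, 30, 90, 150 and 180 (Table 2).

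**Assumed, not in the documents.** PHQ-9 benefit 1.5 points; between-caregiver SD 4; residual SD 3; caregiver slope SD s from 0 to 0.3 points per month, correctly modelled (the protocol prints a random intercept only); independent caregivers, all bereaved, all six visits complete.

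**1. Standard errors, bereavement visits alone.** In months (days/30), mean visit time is 2.578 and Sxx = 31.35.
- Slope difference: sqrt[(2/164)(9/31.35 + s²)] = 0.0592 (s = 0) or 0.0678 (s = 0.3).
- Six-visit mean difference: sqrt[(2/164)(16 + 9/6 + 2.578² s²)] = 0.462 or 0.470.
- Day-180 difference: sqrt[(2/164)(16 + 9 + 36 s²)] = 0.552 or 0.587.

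Power = Φ(|δ|/SE − 1.96), plus the opposite tail where it is not negligible.

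**2. Results by shape of benefit, transition to day 180.**

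| Benefit (points) | Slope test | Six-visit mean | Day 180 |
|---|---|---|---|
| Constant 1.5 | δ = 0: 5% (2.5% each way) | 1.5/0.462 = 3.25, 1.5/0.470 = 3.19: 89-90% | 72-78% |
| Narrowing 2 to 1 | 0.167/0.0592 = 2.82, 0.167/0.0678 = 2.46: 69-80%, **favouring control** | mean 1.57: about 92% | 40-44% |
| Widening 1 to 2 | 69-80%, favouring intervention | mean 1.43: 86-87% | 93-95% |
| Emerging 0 to 1.5 | 0.25/0.0592 = 4.22, 0.25/0.0678 = 3.69: 96-99% | mean 0.644: 28-29% | 72-78% |

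The 5% is algebra: a constant difference has zero slope, so it holds equally for 4 points (the change quoted in V. Number of Subjects) and for either time origin.

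**3. Sensitivity.** Over between-caregiver SD 3-5 and residual SD 2.5-4, level power for a constant 1.5 points is 72-99%; the slope stays at 5%. Full bereavement follow-up is optimistic: "During study wind down, participants will complete their final data collection measure based on where they are at in the intervention", so some will finish before the death. With 115 per arm level power is 76-78%, and with 82 it is 62-63%. With 82, the narrowing profile favours control in 41-51%.

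**4. Visits pooled from enrolment.** Same SDs and 164 per arm; pre-death visits from Table 2; transition placed at the date of death, between day 30 and day 300. Worked case: death at day 165, s = 0, benefit 1.5 at every visit from day 14. The 11 visits have mean time 5.267 months and Sxx = 152.95. Expected slope difference = 1.5 x 5.267 / 152.95 = 0.0517; SE = sqrt[18/(164 x 152.95)] = 0.0268; ratio 1.93; power about 49%. Over the range of death dates and s, power is about 14-49%. If the benefit starts at transition it is 77% to over 99%. Either way a single line mixes the two phases and cannot separate H1a from H1b.

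**5. The SAP equation.** Its group coefficient is a level contrast at the last measure, but it uses one record per caregiver where the SAP's text describes repeated measures and slopes. Its baseline term is undefined for TRIG, which Table 2 describes as a scale for bereaved people.

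**The case against.** The strongest reply is that this is under-specification, not a wrong test. The stated aim refers to whole profiles, the model is labelled MMRM, and arm-specific intercepts and slopes yield a level difference at any chosen time. The slope wording is one explanatory sentence, and the sample size section itself refers to a change in PHQ-9. That is fair as far as it goes: a level contrast could be derived. But none is declared, and the only quantities named are the slopes.

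Three stronger readings are tempting and are not supported.

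- *That no level test is prespecified, so one would have to be invented after the data are seen.* The SAP's group effect on the final measure is such a test. The problem is an unresolved conflict between and within the documents.
- *That the slope analysis will miss a sustained bereavement benefit.* This needs bereavement visits modelled alone. That is the natural reading for TRIG but only one open reading for PHQ-9 and GAD-7, because H1a and H1b share one printed model with no split by phase. Pooled from enrolment, the slope has some power.
- *That TRIG has no baseline.* Table 2 does not list instruments by visit, so the documents show only that the term is undefined.

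Nor is the slope always the weaker test. It is much stronger if the benefit emerges only after transition. The narrowing profile is an illustration, not a prediction. The SAP may also simply be out of date, but nothing in either document says so.

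**Conclusion.** The concern holds in this form: the hypotheses are about levels, the only inference the protocol names is about slopes, and the SAP's level contrast contradicts both its own narrative and the protocol. Confidence is high in the mismatch and the conflict. It is lower in any predicted loss, which depends on the visit set and the shape of the benefit.

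On bereavement visits alone, the 5% rejection rate for a constant benefit needs no variance assumption. The 89-90% comparison, the 69-80% probability of a result favouring control, and the pooled figures rest on the assumed SDs, effect sizes, independence and complete follow-up. This should be fixed before analysis.

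**What to change.** In both documents, for each of H1a, H1b and H2:

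1. State which visits enter the model (for example pre-death for H1a, bereavement for H1b and H2) and the time origin.
2. Name one between-arm level contrast from the repeated-measures model as the test: the adjusted mean difference averaged over stated visits, or at a stated visit. Keep the slope difference as supporting.
3. Adjust PHQ-9 and GAD-7 for their own enrolment scores. Do not use transition scores as baselines, since they follow randomisation and exposure. Adjusting TRIG for enrolment PHQ-9 is optional.
4. Replace the SAP equation with the model chosen, and state which document governs.

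**Cost.** Wording in two documents and modest programming; no new data. The price is power if the benefit emerges only after transition: slope 96-99%, against 28-29% for the six-visit mean and 72-78% at day 180. The choice of level contrast also matters. For a constant 1.5 points (s = 0, unadjusted), day 180 has 78% and the average 90%. Adjusting for enrolment PHQ-9 raises these to 82-94% and to between 94% and over 99%, if the stable part of a caregiver's score correlates 0.5 to 1 between enrolment and bereavement (assumed).

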### **V. Number of Subjects**

1. The anticipated enrollment number is 468 subjects (or 234 for intervention group and 234 for control).
2. The PHQ-9 is widely used, has good internal consistency, is well validated, and is commonly used to inquire about the degree to which an individual has experienced depressed mood over the past two weeks. Our power calculations based on our preliminary work hold the following assumptions: 1) attrition rate of 30% 2) 80% power

3) a two-sided alternative for group differences at the 0.05 level of significance for a change in PHQ-9 scores (average of 4 points, variance of 5.5).

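### The mediation analysis of social support inherits a covariate rule based on balance between arms, which cannot find confounders of the support-to-outcome path, and no visit order is set

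*Protocol*

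**What the plan says.** **Mediation.** Under Statistical Analysis, both documents give the method in one sentence: "Additionally, we will examine how social support mediates our outcomes of interest (depression, anxiety, and grief intensity"). Neither gives a mediator model, an indirect-effect estimator, a visit order, a list of mediator-outcome confounders or a sensitivity analysis. The displayed equations contain no mediator term.

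**Covariates.** The next sentence in each document says that covariates enter as set out earlier. The earlier rule, in the Protocol's Data Analysis Plan and repeated in the SAP's Statistical Assumptions, is "Additional confounders will only be introduced as covariates if we find evidence of imbalance between groups at baseline". The trigger is a chi-square or t-test between arms: "Variables that differ significantly between groups will be included in regression models as potential confounders".

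**Always included.** The Protocol adds "We will include time from study enrollment to the last observation as a covariate, as well as hospice agency". The SAP always includes time since enrolment, and its equation always contains the baseline value of the outcome.

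**Timing.** Table 2 of the Protocol gives one survey schedule with no separate timing for mediators. The SAP takes the last available value of each outcome.

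**Status of the claim.** The Protocol writes mediation by social support into H1a and H1b. The SAP words both as plain arm comparisons and leaves mediation to the separate sentence.

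**The concern.** Randomisation makes the arms comparable. It does not make caregivers with high support comparable with caregivers with low support. Anything that shapes both support and mood, such as support at enrolment, relationship to the patient or living with the patient, confounds the support-to-outcome path even when the arms are perfectly balanced. The Protocol's Subgroup Analysis itself names relationship and residence as possible influences on burden, yet the rule would normally leave them out of a mediation model.

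If mediator and outcome come from the same survey, low mood that depresses reported support looks the same as low support that depresses mood.

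At stake is the explanation of how the intervention works, on which the conceptual model in section I of the Protocol rests. An intervention designed to raise support could be credited with working through support merely because support and PHQ-9 are correlated.

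**Working it through.** **1. Does the screen look in the right place?** A confounder of the support-to-outcome path has the same expected distribution in both arms. A between-arm test at 0.05 therefore flags it about 5% of the time, by chance. In simulation the true common cause was flagged in about 4–6% of trials.

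**2. Inputs.**
- From section V of the Protocol: "The anticipated enrollment number is 468 subjects (or 234 for intervention group and 234 for control"), 30% attrition and two-sided 0.05. Analysed: 468 × 0.70 = 327.6, taken as 327 or 328.
- The documents give no figure for the mediation analysis, so there is none to reproduce.
- Assumed: true effect of support on outcome is zero; ICC 0.6 for both scales; correlation of the stable components (r_s) −0.3 to −0.5; same-visit residual correlation (r_e) 0 to −0.3; PHQ-9 SD 5; the arm raises support by a = 0, 0.2 or 0.4 SD; the mediator is taken at the same visit and added to the SAP equation.

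**3. Size of the spurious effect.** Let M be support, Y the outcome and Y0 its baseline, each with SD 1 within arm.
- cov(M,Y) = 0.6·r_s + 0.4·r_e; cov(M,Y0) = 0.6·r_s; corr(Y,Y0) = 0.6.
- The coefficient of M, whose true value is 0, becomes b = [cov(M,Y) − 0.6·cov(M,Y0)] / [1 − cov(M,Y0)²].
- Weakest case (r_s = −0.3, r_e = 0): b = (−0.18 + 0.108)/(1 − 0.0324) = −0.074. Indirect effect at a = 0.4: 0.4 × (−0.074) × 5 = −0.15 PHQ-9 points.
- Strongest case (r_s = −0.5, r_e = −0.3): b = (−0.42 + 0.18)/(1 − 0.09) = −0.264. Indirect effect: 0.4 × (−0.264) × 5 = −0.53 points.

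So adjusting for the baseline outcome reduces the bias but does not remove it.

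**4. How often mediation is declared.** A false finding needs the arm-to-support path to be detected, so power for that path is roughly a ceiling. SE = 2/√327 = 0.1106 SD. At 0.4 SD, z = 3.62 and Φ(3.62 − 1.96) = 0.95. At 0.2 SD, z = 1.81 and Φ(1.81 − 1.96) = 0.44. The simulated rates (product-of-coefficients test, range over the assumed correlations) fit this:

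| Rise in support | Ceiling | False mediation |
|---|---|---|
| 0.4 SD | 95% | about 20–95% |
| 0.2 SD | 44% | 5–42% |
| none | 5% | at most about 5% |

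**5. Reverse direction.** Suppose the arm lowers the outcome by 0.3 or 0.5 SD, the outcome lowers reported support (coefficient −0.3 or −0.5), and support does nothing. A same-visit model then declares mediation in 14–63% of trials. An earlier-visit mediator with adjustment for both baselines and for the outcome at the mediator visit gives under 1%.

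**6. Does lagging cure stable confounding?** In the step 2 scenarios at 0.4 SD, an earlier-visit mediator with enrolment mediator, enrolment outcome and outcome at the mediator visit gave 2–12%. With a stable correlation of −0.8, about 50% remained. In a separate setting, where one common cause drove all stable variation in both scales (correlation −0.3), the same kind of model gave 52% (0.3 SD rise) and 79% (0.5 SD rise). The rate fell to 4–5% only when the common cause itself was in the model.

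**The case against.** The strongest reply is that neither document writes a mediation model, so no faulty model can be attributed to the plan, and the error rates belong to a model that had to be supplied. That stands as far as it goes: the plan does not prescribe a same-visit mediator, although the single schedule and the last-observation rule lean that way. But the covariate rule is stated and directly follows the mediation sentence. It is the wrong rule for this purpose, which is more than missing detail.

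A reader might infer four stronger things that the documents do not support:

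- **That only variables differing between arms are adjusted for.** Time to last observation and agency always enter under the Protocol, and the baseline outcome always enters in the SAP equation. They do not remove the bias.
- **That false mediation is to be expected whatever happens.** It requires measured support to rise in the intervention arm, directly or because better mood raises reported support. The size of that rise is not in the documents, and the rate falls quickly as it shrinks.
- **That the efficacy result is compromised.** The arm comparisons do not involve the mediator. The sample size in section V rests on group differences in PHQ-9, and the SAP already words H1a and H1b as arm comparisons.
- **That ordering the visits solves the problem.** Step 6 shows otherwise.

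**Conclusion.** The concern holds for the mechanism claim only. The inherited covariate rule cannot select the confounders that mediation needs, and nothing puts the mediator before the outcome. If the intervention raises measured support, the plan can report that support carried the effect when it carried none: in about 20–95% of trials at a 0.4 SD rise and 5–42% at 0.2 SD, but no more than about 5% with no rise. These rates rest on the assumed ICC, correlations and same-visit mediator in step 2, none of which is in the documents. That the screen examines the wrong comparison does not depend on them. Because the randomised comparisons of PHQ-9, GAD-7 and grief are untouched, this should be fixed but does not threaten the primary result.

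**What to change.** In the Protocol's Data Analysis Plan and in both statistical sections of the SAP:

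1. Exempt mediation models from the imbalance rule.
2. State that they always include the enrolment mediator score, the enrolment outcome score, the outcome at the mediator visit, and named mediator-outcome confounders whatever the balance between arms: caregiver age, relationship, residence with the patient and agency. Grief is measured only in bereavement and has no enrolment score, so use enrolment PHQ-9 there.
3. Take the mediator at an earlier survey than the outcome, for example day 30 and day 90.
4. Report the indirect effect with a bootstrap interval and a sensitivity analysis for residual mediator-outcome confounding. The sensitivity analysis is essential, since lagging and baseline adjustment do not remove strong stable confounding.
5. Align the Protocol's H1a and H1b with the SAP, so that they are judged on the arm comparison and mediation is a secondary question.

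**Cost.** The change is to wording. PHQ-9, GAD-7 and the listed mediators are already on the survey schedule, and the named covariates already appear in the Protocol's analysis plan. Caregivers without two follow-up surveys drop out of the mediation model, and the indirect effect is estimated less precisely.

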### Statistical Analysis

**H1a:** Family caregivers receiving the Caregiver Speaks intervention will report lower levels of depression and anxiety compared to those in the control group during active caregiving.

**H1b:** Family caregivers receiving the intervention will report lower levels of depression and anxiety compared to those in the control group during bereavement.

**H2:** Bereaved family caregivers receiving the intervention will report lower levels of grief intensity compared to those in the control group.

We will examine differences between longitudinal profiles of the two study groups for each of the outcomes (PHQ-9, GAD-7, social support, & grief intensity). We will use mixed (hierarchical) models with repeated outcome measures nested within participants (see model below). This will allow us to draw inferences about how our outcome measures (PHQ-9, GAD-7 & grief intensity) change over time (slope) between the two study groups. Mixed models are able to accommodate differing numbers of measurements at varying time intervals for participants. Additionally, we will examine how social support mediates our outcomes of interest (depression, anxiety, and grief intensity). As described above, we will also include covariates where indicated.

**Last post-baseline measure =  $\beta_0 + \beta_1[\text{study group}] + \beta_2[\text{baseline measure}] + \beta_3[\text{time since enrollment}]$**

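### The protocol's mixed model adjusts for enrolment PHQ-9 or GAD-7 only if a balance test is significant, whereas the SAP's equation always adjusts

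*Protocol*

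**What the plan says.** **Protocol, Data Analysis Plan, Statistical Analysis.** The mixed model for H1a and H1b has a separate mean intercept and linear slope in each arm plus a random intercept per caregiver. The arm coefficients "represent the slopes for the treatment and control group respectively with intercepts that vary about the respective mean intercepts". Inference is said to concern how outcomes change over time, through the slopes. No term for the enrolment score appears.

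**Protocol, Statistical Assumptions.** Two covariates are always included: "We will include time from study enrollment to the last observation as a covariate, as well as hospice agency". For the rest, "Additional confounders will only be introduced as covariates if we find evidence of imbalance between groups at baseline". Baseline measures are compared by t-test or chi-square, and those that differ significantly are added. The Statistical Analysis text carries this rule into the mixed model.

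**SAP, Statistical Analysis.** The prose also describes a mixed model, but the printed equation is a regression of the "Last post-baseline measure" on study group, baseline measure and time since enrolment. There the baseline measure is unconditional.

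**Protocol, Table 2.** Pre-bereavement surveys fall at baseline and days 14, 30, 90 and 150, then every 6 weeks. Post-death surveys fall at transition and days 14, 30, 90, 150 and 180. Neither document says which surveys enter the H1a and H1b models, or where time zero lies in bereavement.

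**The concern.** A caregiver's enrolment score on the same scale is likely to be a strong predictor of later scores, and the plan already collects it. The reason to adjust is its prognostic value, not an observed imbalance. A significance test on a randomised baseline detects only chance. When it is negative, the available precision is given up and any smaller imbalance stays in the comparison. When it is positive, the primary model has been chosen by the data.

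At stake are the width of the PHQ-9 and GAD-7 intervals, some sensitivity of the arm comparison to chance imbalance, and which model is primary, since protocol and SAP print different ones.

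**Working it through.** **Inputs.** Section V gives the size: "The anticipated enrollment number is 468 subjects (or 234 for intervention group and 234 for control" per arm, with "attrition rate of 30"%. Evaluable: 468 × 0.70 = 327.6, about 164 per arm. Survey days are from Table 2. The within-person correlation is in neither document, so every correlation below is an assumption. The calculations take complete data and a random-intercept structure.

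**The plan's own figure.** There is no stated precision for this model to reproduce. The sample size itself does not follow from its stated inputs ("average of 4 points, variance of 5.5"). As written, 2 × (1.96 + 0.84)² × 5.5 / 4² = 5.4, so 6 per arm. Reading 5.5 as an SD gives 29.7, so 30 per arm. That is a separate matter and does not bear on this point.

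**H1a, slope contrast.** Take total variance 1, intraclass correlation ρ, and k surveys at days t. Per-caregiver information is:
- I00 = k / (1 + (k−1)ρ)
- I01 = Σt / (1 + (k−1)ρ)
- I11 = [Σt² − ρ(Σt)² / (1 + (k−1)ρ)] / (1−ρ)

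Setting the arm difference in intercepts to zero cuts the variance of the slope difference by I01² / (I00 × I11). For days 0, 14, 30, 90, 150 and ρ = 0.5: Σt = 284, Σt² = 31,696 and the denominator is 3. So I00 = 1.667, I01 = 94.67, I11 = 36,507, and the cut is 94.67² / (1.667 × 36,507) = 0.147. Interval width falls by 1 − √(1 − 0.147) = 7.7%.

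| ρ (assumed) | Variance cut, to day 150 | Narrower interval, to day 150 | Variance cut, to day 30 |
|---|---|---|---|
| 0.4 | 19.3% | 10.2% | 32.3% |
| 0.5 | 14.7% | 7.7% | 26.4% |
| 0.6 | 10.9% | 5.6% | 20.7% |
| 0.7 | 7.6% | 3.9% | 15.2% |

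**What the balance test leaves unadjusted.** Assuming a 5% test, the largest non-significant difference is 1.96 × √(2/n): 0.18 SD at 234 per arm and 0.22 SD at 164 per arm. In H1a with free intercepts and ρ = 0.5, each 1 SD of imbalance moves the slope contrast by −0.27 SD over 150 days and the fitted day-150 difference by +0.43 SD. An unflagged 0.2 SD therefore moves them by about −0.05 SD and +0.09 SD.

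**H1b, if only post-death surveys enter.** With correlation r between the enrolment score and a post-death score, adjustment multiplies the variance of a one-visit contrast by 1 − r². For r = 0.4 to 0.6 the cut is 0.16 to 0.36. The share of an unflagged imbalance that reaches an unadjusted level contrast is r times its size: 0.4 × 0.18 = 0.07 SD to 0.6 × 0.22 = 0.13 SD. For the slope contrast there is no gain. With 164 per arm and a within-phase correlation of 0.6, the standard error of the slope difference over 180 days is 0.075 SD with or without the covariate.

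**A limit on the obvious repair.** One shared intercept with a linear trend forces the arm difference to grow from zero in proportion to time. If a constant effect were present from day 14, that model would fit only about 6 to 7% of it at day 14 and 67 to 78% at day 150 (ρ from 0.7 to 0.5).

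**The case against.** The best defence has five parts.

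- **The protocol does provide for adjustment.** Baseline measures that differ significantly are added. This stands: a reader might infer that the model never adjusts, and the text does not support that. The defect is that adjustment is conditional on a test.
- **H1a probably already uses baseline**, as the response at time zero, and the free-intercept contrast is unbiased over randomisation. This also stands. The loss is of efficiency and of robustness to chance imbalance, not of validity, and over 150 days it is modest.
- **For H1b the protocol names slopes**, and a baseline main effect does nothing for a slope. This stands too. A reader might infer wider intervals in both phases whatever the contrast; that is not so. But the hypotheses speak of lower levels of depression and anxiety, and for a level contrast the gain is real.
- **The absence of the enrolment score from H1b is inferred** from the survey schedule and is nowhere stated. Correct, so the H1b figures are conditional on that reading.
- **The planned effect would be detected anyway.** With 164 per arm, even an SD of 5.5 gives over 99.9% power for 4 points. True, but 80% power corresponds to (1.96 + 0.84) × √(2/164) = 0.31 SD, or 1.7 points at SD 5.5. Precision matters for effects near that size and for the 95% intervals that the plan promises.

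None of this answers the conflict between the two documents.

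**Conclusion.** The point holds in limited form. The protocol does not prespecify adjustment for the enrolment PHQ-9 or GAD-7 in H1a and H1b; the SAP's equation does. The test-triggered rule gives up available precision and leaves chance imbalances of up to about 0.2 SD in the comparison.

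For the H1a slope difference the avoidable variance is about 8 to 19% with visits to day 150 and 15 to 32% with visits to day 30, for assumed correlations of 0.7 down to 0.4. For H1b it is 16 to 36% for a level contrast at one visit, for an assumed correlation of 0.4 to 0.6 and post-death visits only, and nil for a slope contrast.

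The argument also rests on the baseline score being unaffected by knowledge of the arm, which the protocol leaves unclear. Section II randomises upon consent and Table 1 places randomisation before the orientation meeting. Section III sends the baseline link after the consent meeting, yet the statement attached to that survey speaks of randomisation as still to come.

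**What to change.** In the protocol's Statistical Analysis text and in the SAP:

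1. For H1a, model post-baseline scores with the enrolment score of the same scale as a fixed covariate, whatever a balance test shows. Alternatively, use a common baseline mean across arms with visit as a category, not one linear trend through a shared intercept.
2. For H1b, model post-death scores with the same fixed covariate. State which surveys enter each model and where time zero lies.
3. Define the arm contrast as a difference in levels, to match the hypotheses.
4. Remove the significance-test trigger for these scores.
5. Print one model in both documents.
6. Confirm that the baseline survey is completed before the caregiver learns the assigned arm, and say how scores completed later are handled.

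The cost is wording and a check of survey dates against the time of allocation. No extra participants, visits or measures are needed. If some baseline scores prove to have been completed after the arm was known, the gain is smaller.
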